# **Trial Procedure**

Once parental consent is collected, the research team will visit the school to supervise participants' registration to the intervention (i.e. day one). The registration process will be completed online, during class time, using a computer/mobile/ or tablet device. Registration is estimated to take no more than 20-30 minutes. Although registration is completed privately by the student, a researcher or trained school staff member will be present to answer any questions and offer assistance. Baseline measures will be collected during this online registration process. Once all students have registered and completed the baseline assessment, a list of student names, alongside their trial identification numbers, will be given to the school counsellor. This will be used when the school counsellor is required to follow-up with a student as the email alerts do not contain student names (only the trial identification numbers). Throughout the trial, students will be able to use the intervention at their own leisure, either in or out of school time. Participants will also receive two optional monitoring questionnaires which are delivered via email (with SMS reminder) at day 15 and day 29. At day 43, a researcher will return to the school to collect the final endpoint measures using the same procedure for registration.

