# **Treatment of Subjects**

#### Intervention

**Name**: Smooth Sailing (Arm 1). Intervention codes: Early detection/screening and Treatment (other) (behavioural intervention)

Smooth Sailing is an online mental health service designed and administered by the Black Dog Institute. It is based on the principles of "stepped care" such that the intensity of the recommended interventions is matched to individuals' symptom severity and individuals "step up" if they have not responded to treatment after a set period of time. Exposure to Smooth Sailing involves:

- 1. Registration & Mental Health Assessment. In class time, participants are given a slip of paper with the service URL and their unique identification code. They then use a school or personal internet device to visit this website and undertake registration. Before registration commences, participants are asked to complete the Gillick Competency measure which consists of X questions to further confirm their understanding of the service and study requirements. Upon correct completion of this, participants are invited to create a personal profile (name, date of birth, email address, mobile phone number, and gender, history of mental health issues, and use of the internet for mental health information). Once a personal profile is created, four questionnaires were used to measure the presence of depression, anxiety, help-seeking attitudes and behaviours (see Appendix B in Attachments section of ANZCTR record). This takes approximately 30 minutes to complete.
- 2. Step allocation. Based on the answers inputted during registration, Smooth Sailing allocates each participant to one of five "steps". This is automatic and based on a clinical algorithm which accounts for the severity levels of the anxiety and depression symptoms as reported by the participant on the Generalised Anxiety Disorder Scale (GAD-7) and the Patient Health Questionnaire (PHQ-9). Each "step" matches a severity level and was based on clinical practice guidelines. The step allocations were: Nil/minimal (Step 0), Mild (Step 1),

Moderate (Step 2), Moderately Severe (Step 3), and Severe (Step 4). Please see Table 1 for more detail.

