- 4. Monitoring and Feedback. At two points in the study (Day 15 and Day 22) participants received an automated 18-item "monitoring questionnaire" to assess how they were doing. This consisted of the Goldberg Depression and Anxiety Scales and was delivered via email or SMS. An automated thank you message was received alongside a reminder to use the program if participants completed this questionnaire.
- 5. Reassessment (Post-test/endpoint): At Day 43, researchers revisited the schools. Participants again logged onto the service using the same URL and unique ID codes and were delivered the final endpoint questionnaires. In theory, the results of these questionnaires would be used to determine whether a participant had responded to care or needed to be "stepped up". In accordance with the Clinical Practice Guidelines for the Treatment of Depression in Young Adults, if a participant has not responded to their care within 43 days of their baseline allocation, they would be "stepped up" to the next level of care. See Table 3 below for the stepping matrix at 43 days. The matrix was designed such that a participant would not be stepped down, instead will either remain at the same step or step up. However, as the current trial ceased at 43 days, no stepping occurred during this trial. Instead, this trial was

designed to provide the clinical data necessary to determine whether the steps are feasible for future trials.

Throughout the trial, participants will be obligated to use Smooth Sailing at pre-test (for registration and baseline measure collection) and again at post-test (for reassessment and final endpoint collection) only. Completion of the monitoring questionnaires and use of the other components is entirely voluntary, and will be a measured as part of the study.

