**Table 1. Step Allocation Criteria** 

Step	Severity Level	Criteria
Step 0 &	Nil, minimal	PHQ9 (0 - 4) & GAD7 (0 - 4)
Step 1	Mild	PHQ9 (5 - 9) & GAD7 (0 - 9)
		OR
		PHQ9 (0 - 9) & GAD7 (5 - 9)
Step 2	Moderate	PHQ9: (0-14) & GAD7: (10-14)
		O R
		PHQ9: (10-14) & GAD7: (0-14)
Step 3	Moderately	PHQ9: (0-19) & GAD7:(15-19)
	Severe	OR
		PHQ9: (15-19) & GAD7: (0-19)
Step 4	Severe	PHQ9: (0-27) & GAD7: (20-21)
		O R
		PHQ9: (20-27) & GAD7: (0-21)

Table 2. Care delivered at each step

Step	Severity Level	Care provided
Step 0 and 1	Nil, minimal, mild	Online psycho-education: This consists of written text, videos, and activities created by Black Dog Institute researchers. It also includes URL links to other psycho-education material published by reputable Australian mental health organisations including headspace, Reachout, beyondblue and SANE Australia. It is estimated that 60% of participants will be allocated to this step at baseline.
Step 2	Moderate	Self-directed online cognitive behavioural therapy (CBT) in addition to the online psycho-education material. The online CBT programs that will be offered by Smooth Sailing are evidence-based, produced by Australian university research groups, and free to access. The programs include MoodGym (Australian National University), and Brave Online (University of Queensland). It is estimated that up to 25% of participants will be allocated to this step at baseline.
Step 3	Moderately Severe	Self-directed online cognitive behavioural therapy (CBT) in addition to the online psycho-education material and additional support from the school counsellor. This support will be offered face-to-face by a school counsellor. In the current study, any participant who reports moderate symptoms will trigger an electronic notification alert which will be automatically sent to the school counsellor or head teacher for further investigation. This will allow the school counsellor to facilitate a face-to-face session to provide the

		counselling or refer on to external services. It is estimated that between 10-15% of participants will be allocated to this step at baseline.

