Step 4	Severe	Self-directed online cognitive behavioural therapy (CBT) in addition to the online psycho-education material and additional support from the school counsellor. In the current study, any participant who reports moderate symptoms will trigger an electronic notification alert which will be automatically sent to the school counsellor or head teacher for further investigation. This will allow the school counsellor to facilitate a face-to-face session to provide the counselling or refer on to external services. It is estimated that 5% of participants will be allocated to this step at baseline.

Throughout the trial, the school counsellor will be physically located within the school that the participant attends. He or she has a background in counselling or psychology and is present at the school at least two days per week. The school counsellor will provide clinical support to any participant that reports moderately severe or severe depression/anxiety scores, or reports suicidal ideation throughout the study. See Assessment of Efficacy for details on how service use, adherence, and satisfaction will be measured.

Table 3. Step Allocations at Day 43 based on Step at Baseline

	Step at Baseline	1	2	3	4
Step at 43 days					
1		1	2	3	4
2		2	3	3	4
3		3	3	4	4
4		4	4	4	4

Comparator: No control group as it is an uncontrolled trial.

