#### Post-test/Final endpoint Assessment

At day 43, participants will return to the website to complete the online battery of questionnaires including the: Patient Health Questionnaire (PHQ-9); Generalised Anxiety Disorder Questionnaire (GAD-7); the General Help Seeking Behaviour Questionnaire and Actual Help-seeking Behaviour Questionnaire and the Satisfaction Questionnaire for Students Acceptability and demand measured by: The number of youth and parents who consented to the study; The number of modules completed; The number of students who reported using the online CBT programs; The number of students who completed the fortnightly check-in questionnaires;

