# **Assessment of Safety**

#### **Outcomes Advisory Group**

An Outcomes Advisory Group has been established to provide specific monitoring, governance, and reporting of adverse events and trial safety. This group consists of the trial manager, the lead investigators, and the medical expert. This team meets every two weeks, and on an as-needed basis, to monitor the safety of the trial. A data safety monitoring board will not be utilised in the current study. This decision was made on the basis of two key factors:

- 1. The current study targets a non-clinical population, and does not target a high risk sample.
- 2. The research platform used in the trial has an alert system which provides timely feedback to research personnel, so that distressed participants can be identified and attended to straight away. Once identified, school counsellors will be made aware of the distressed participant, so that they may provide immediate and, if necessary, ongoing assistance. This procedure ensures the highest level of care for participants, as school counsellors are appropriately trained, familiar, accessible, and available to assist should such a scenario eventuate.

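### A severe score on the two mid-trial Goldberg questionnaires has no stated route to the school counsellor, although the promised support and the alert system are not limited to the supervised sessions

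*Protocol*

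**What the plan says.** Trial Procedure announces "two optional monitoring questionnaires which are delivered via email (with SMS reminder) at day 15 and day 29". Intervention, item 4, identifies the instrument as the 18-item Goldberg scales, dates the second questionnaire Day 22 instead, and gives the purpose as finding out how students are doing. The response it states is: "An automated thank you message was received alongside a reminder to use the program if participants completed this questionnaire". The one study use given for these forms is a feasibility count: "The number of students who completed the fortnightly check-in questionnaires" (Post-test/Final endpoint Assessment).

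Care and alerts are tied to other instruments. Item 2 reads: "Based on the answers inputted during registration, Smooth Sailing allocates each participant to one of five" steps, using the PHQ-9 and GAD-7. Item 3 notifies the counsellor of anyone placed in Step 3 or 4, and item 5 says that no stepping took place in this trial. The section on responding to risk of significant harm ties counsellor notification to the baseline and follow-up questionnaires. The table of potential adverse events sets the triggers at PHQ-9 or GAD-7 of 15 or more, and PHQ-9 item 9 of 1 or more.

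Two statements carry no such limit. The paragraph on the counsellor's role promises support to "any participant that reports moderately severe or severe depression/anxiety scores, or reports suicidal ideation throughout the study". Outcomes Advisory Group gives, as the second of two reasons for having no safety board, an "alert system which provides timely feedback to research personnel, so that distressed participants can be identified and attended to straight away".

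**The concern.** A symptom questionnaire sent to adolescents invites them to disclose distress. Inclusion Criteria admits students with current suicidality, and Type of Endpoint makes showing safety one of the trial's aims. If a student reports marked worsening at Day 15 and the platform replies only with thanks and a reminder, the trial holds the information without a stated duty to use it. The promise of support and the reason for having no board would then reach further than the procedure that is meant to deliver them. Between the two supervised sessions, the declared safety route would be the school-report route in the table of additional adverse events, which needs the student or the school to raise the problem.

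**Working it through.** No statistic in the protocol bears on this point, so the check is a comparison of texts with some calendar arithmetic.

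**1. Scheduled symptom assessments against stated alert rules**

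| Assessment | Instrument | Setting | Stated alert rule |
|---|---|---|---|
| Day 1 | PHQ-9, GAD-7 | Class, supervised | Yes: Step 3 or 4; score of 15 or more; item 9 of 1 or more |
| Day 15 | Goldberg | Email or SMS, optional | None stated |
| Day 29 (or Day 22) | Goldberg | Email or SMS, optional | None stated |
| Day 43 | PHQ-9, GAD-7 | Class, supervised | Yes, through the risk-of-harm procedure; the adverse event table itself names baseline only |

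The stated alert procedure covers 2 of the 4 assessments. The interval between those two is 43 − 1 = 42 days.

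**2. Text that might close the gap**

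- The care table says that "any participant who reports moderate symptoms will trigger an electronic notification alert", without naming an instrument or a time. The words stand in the Step 3 and Step 4 rows, and the step criteria are PHQ-9 and GAD-7 ranges. They do not show that a Goldberg score is included.
- The paragraph on the counsellor's role covers the whole study in its wording. It shows intent but names no Goldberg threshold and no step by which a score reaches the counsellor.
- The Duty of Care section applies to self-reported risk during the study. The procedure that follows is built on the pre-test and post-test measures.
- The same procedure allows questionnaires only in supervised class time. The emailed forms do not fit that rule, so it gives them no route either.
- The table of additional adverse events offers a real route, but one that does not use the score.

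**3. Wait until the next assessment with a defined alert, if no other route acts**

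- Reported at Day 15: 43 − 15 = 28 days.
- Reported at Day 29: 43 − 29 = 14 days.
- Reported at Day 22: 43 − 22 = 21 days.

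The feasibility count calls the questionnaires fortnightly. With Day 29 the gaps are 15 − 1 = 14, 29 − 15 = 14 and 43 − 29 = 14. With Day 22 the gap after Day 15 is 22 − 15 = 7. Day 29 fits, which favours the 14-day figure.

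**4. Who could be exposed**

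The care table expects 60% in Steps 0 and 1 and up to 25% in Step 2. Of the recruitment target of 106 that is at most 0.85 × 106 = 90.1, about 90 students. Unless item 9 is positive, they generate no counsellor alert at baseline. This is the size of the group in which new worsening could go unseen. It is not a forecast of how many would worsen, because no completion or worsening rate is given.

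**5. Counsellor availability**

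The counsellor "is present at the school at least two days per week". Assume a five-day school week and exactly two days on site. The two gaps between on-site days then sum to 7. The longer gap is at least 4 days (Monday and Thursday: 3 + 4) and at most 6 (Monday and Tuesday: 1 + 6).

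**The case against.** The strongest reply is that this is a claim about absence, while the place most likely to hold the rule is not at hand. The protocol refers to a supplementary document with flowcharts for risk of harm, and leaves instrument detail to an appendix. That stands, and it is why the point is confined to what the protocol states. If the rule exists there, a cross-reference in item 4 settles most of the matter.

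Second, restricting alerts to supervised sessions can be defended. The protocol wants sensitive questions answered where the counsellor can be reached quickly, and alerts from answers given at home could arrive on days when the counsellor is away. That is a fair design argument, but the protocol does not make it for the Goldberg forms, and its unrestricted promise of support points the other way.

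Third, the students at highest risk at entry are already referred, with a check by the trial manager within 48 hours, and school reports continue throughout. This narrows the exposed group to students not flagged at baseline who worsen, choose to answer, and are not noticed by the school. It does not remove the gap.

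Three stronger readings are tempting and are not supported:

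- A reader might infer that nobody would be told of a severe mid-trial score. Item 4 states what the student receives; it does not say that no one else is informed.
- A reader might infer that the count of email triggers in Summary of Potential Adverse Events reflects only the two supervised sessions. That text speaks of triggers over the study period, so the restriction would be an inference from the missing Goldberg rule.
- A reader might infer that the decision to have no safety board fails. The sentence on the alert system speaks mainly to speed and is one of two reasons, the other being a non-clinical population. The Outcomes Advisory Group meets every two weeks in any case.

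**Conclusion.** The point holds as a gap in the stated procedure and should be fixed. The protocol states no Goldberg cut-off or notification, and no route from a severe mid-trial score to the counsellor, while its promise of support and its description of the alert system are not confined to the supervised sessions. Followed as written, a severe self-report could wait 14 to 28 days for the next assessment with a defined alert.

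This rests on three assumptions: that the supplementary risk-of-harm document adds no rule, that neither the student nor the school raises the problem first, and that follow-up alerts operate at Day 43 as the risk-of-harm procedure says. Confidence is medium, chiefly because of the first. The consequence is for participant safety and for the evidence behind the safety aim; the pre-post comparison of help-seeking scores does not change.

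**What to change.** In Intervention, item 4, state that a Goldberg score above a cut-off set in advance by the Clinical Advisory Group triggers the existing email alert to the school counsellor and the trial manager. Name the head teacher, whom the care table already allows as a recipient, for days when the counsellor is off site. Apply the existing 48-hour check, and add these alerts to the two-weekly report to the Outcomes Advisory Group. Show the student helpline details in adapted wording: the present pop-up was written for a positive suicidal-ideation item and should not be reused unchanged. Correct the second date so that both sections agree; Day 29 fits the fortnightly schedule.

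If alerts on these forms are not wanted, say in item 4 that monitoring scores are not acted on, and tell students so on the form. Then limit the alert rationale under Outcomes Advisory Group, and the score-based count under Summary of Potential Adverse Events, to baseline and Day 43. If the supplementary document already holds a rule, cite it in item 4.

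The first option costs protocol wording, one scoring rule on the existing platform, and one more line in an existing report. Its downsides are some extra alerts for counsellors, partial data because completion is optional, and slower response to unsupervised answers. At the minimum attendance the longest wait for an on-site day is 4 to 6 days, still shorter than 14 to 28. The second option costs wording only, but leaves the gap in place and declares it.

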**Table 1. Step Allocation Criteria** 

Step	Severity Level	Criteria
Step 0 &	Nil, minimal	PHQ9 (0 - 4) & GAD7 (0 - 4)
Step 1	Mild	PHQ9 (5 - 9) & GAD7 (0 - 9)
		OR
		PHQ9 (0 - 9) & GAD7 (5 - 9)
Step 2	Moderate	PHQ9: (0-14) & GAD7: (10-14)
		O R
		PHQ9: (10-14) & GAD7: (0-14)
Step 3	Moderately	PHQ9: (0-19) & GAD7:(15-19)
	Severe	OR
		PHQ9: (15-19) & GAD7: (0-19)
Step 4	Severe	PHQ9: (0-27) & GAD7: (20-21)
		O R
		PHQ9: (20-27) & GAD7: (0-21)

Table 2. Care delivered at each step

Step	Severity Level	Care provided
Step 0 and 1	Nil, minimal, mild	Online psycho-education: This consists of written text, videos, and activities created by Black Dog Institute researchers. It also includes URL links to other psycho-education material published by reputable Australian mental health organisations including headspace, Reachout, beyondblue and SANE Australia. It is estimated that 60% of participants will be allocated to this step at baseline.
Step 2	Moderate	Self-directed online cognitive behavioural therapy (CBT) in addition to the online psycho-education material. The online CBT programs that will be offered by Smooth Sailing are evidence-based, produced by Australian university research groups, and free to access. The programs include MoodGym (Australian National University), and Brave Online (University of Queensland). It is estimated that up to 25% of participants will be allocated to this step at baseline.
Step 3	Moderately Severe	Self-directed online cognitive behavioural therapy (CBT) in addition to the online psycho-education material and additional support from the school counsellor. This support will be offered face-to-face by a school counsellor. In the current study, any participant who reports moderate symptoms will trigger an electronic notification alert which will be automatically sent to the school counsellor or head teacher for further investigation. This will allow the school counsellor to facilitate a face-to-face session to provide the

		counselling or refer on to external services. It is estimated that between 10-15% of participants will be allocated to this step at baseline.
Step 4	Severe	Self-directed online cognitive behavioural therapy (CBT) in addition to the online psycho-education material and additional support from the school counsellor. In the current study, any participant who reports moderate symptoms will trigger an electronic notification alert which will be automatically sent to the school counsellor or head teacher for further investigation. This will allow the school counsellor to facilitate a face-to-face session to provide the counselling or refer on to external services. It is estimated that 5% of participants will be allocated to this step at baseline.

Throughout the trial, the school counsellor will be physically located within the school that the participant attends. He or she has a background in counselling or psychology and is present at the school at least two days per week. The school counsellor will provide clinical support to any participant that reports moderately severe or severe depression/anxiety scores, or reports suicidal ideation throughout the study. See Assessment of Efficacy for details on how service use, adherence, and satisfaction will be measured.

Table 3. Step Allocations at Day 43 based on Step at Baseline

	Step at Baseline	1	2	3	4
Step at 43 days					
1		1	2	3	4
2		2	3	3	4
3		3	3	4	4
4		4	4	4	4

Comparator: No control group as it is an uncontrolled trial.

